APPENDIX I

Advertising

If the Oral Health Science Center chooses to advertise for subjects, whether in professional or consumer publications, radio, television, or any other means, all advertising must be approved by the IRB prior to use, documented, and retained.

Confidentiality

Subject files will be maintained in a locked location for the duration of the study. The recipients will treat this information confidentially. In the event of any publication regarding this study, subject identity will not be disclosed.

Direct access to study records and source data/documentation, including subject medical records, will be provided as needed to appropriate parties for the purpose of trial-related monitoring, auditing, IRB/IEC review, and regulatory inspection. Prior to participating in the study, subjects will consent, in writing, to the release of their medical records for said purposes.

Data Collection

The Data Manager will supply the paper and/or electronic CRFs to be used in this study. It is the responsibility of the Investigator to maintain and submit accurate and timely CRFs to the Sponsor. All hard copy CRFs will be filled out legibly in ink.

All questions should be answered. For paper CRFs, if an entry requires correction, a single line will be placed through the entry so as not to obscure the original record, the corrected entry will be initialed and dated by the individual making the change, and a reason will be given for the change. There will be no whiteouts or erasures. For electronic CRFs, if an entry requires correction, the change is made directly to the CRF in the database, the user is prompted to provide a reason for the change, and the correction is logged in by an electronic audit trail.

As necessary, the Data Manager may make specified allowable changes to the database without issuing a query to the site, as agreed upon by study site per this protocol. Examples of allowable changes include incorrect date formats, incorrect current year recorded (as in the start of a new year), and unambiguous spelling errors. Changes to common abbreviations and symbols to equivalent text to meet system or coding constraints (e.g., @ = at, ~ = approximately), may also be allowable. Values that are ambiguous or open to interpretation will be queried to the sites. It is the responsibility of the Data Manager to ensure all changes are supported by information contained elsewhere and/or are unambiguous.

Source Documents

The Investigator has the responsibility for ensuring that all source documents (i.e., study and/or medical records) and CRFs are completed and maintained according to the study protocol and are available at the site. Any CRF used as a source document must be identified as such in the Investigator Notebook.

Good Clinical Practices

This study is conducted in compliance with applicable sections of the US Federal Regulations governing informed consent (21 CFR 50), IRBs (21 CFR 56), study conduct (21 CFR 312) and

the International Conference on Harmonization's Good Clinical Practice Consolidated Guidelines, [ICH-GCPs, as published by the FDA on 9 May 1997, Federal Register, Volume 62, Number 90 pages 25691-25709]). During the course of the trial, the clinical site is monitored by P&G staff (Clinical Trial Manager or designee) to ensure compliance with the Protocol, regulations and guidelines, adequacy of the equipment and facilities, and satisfactory data collection.

Informed Consent

A subject consent form will comply with all applicable regulations governing the protection of human subjects. The elements of informed consent and the documentation of informed consent are specified in 21 CFR 50.25 and 50.27 and/or ICH GCPs chapter 4. Each subject must sign and date an informed consent to serve as a participant in the study. A signed copy of the consent form will be given to the subject and a signed copy will be retained by the Oral Health Science Center. Subjects may withdraw from participation in the study at any time. Additionally, the Investigator may withdraw subjects from the study if it is in the best interest of the subjects. The reason for all subject withdrawals from the study will be documented on the appropriate CRF.

Institutional Review

Prior to study initiation, the Investigator must obtain institutional review and approval of both the Protocol and the consent form, in compliance with the US Code of Federal Regulations, Title 21, Part 56 or the ICH-GCPs Consolidated Guidelines, Chapter 3. The Investigator maintains any original authorization letter(s) and forwards copies to P&G. IRB approval letters should include the study title, P&G study number, the address of the IRB, date of request, and the signature of the IRB chairperson/designate. Additionally, the letter must acknowledge that both the Protocol and consent form have been approved by the IRB, with notification of any changes required. The study does not begin until P&G has received written confirmation of IRB approval. This IRB shall also review the investigation at least once a year during study execution. The Investigator notifies the IRB when the study is terminated.

Monitoring

Prior to commencement of the study, an initiation meeting will be held with the appropriate Oral Health Science Center personnel to review the objectives and procedures of the clinical trial. To assure accurate, complete, consistent, and reliable data, the Oral Health Science Center and study procedures will be monitored by a Clinical Trial Manager in accordance with 21 CFR 312 and ICH GCPs Chapter 5.

The Oral Health Science Center study coordinator is expected to contact the Clinical Trial Manager or designee as needed regarding study concerns and/or questions.

Protocol Amendments/Changes

Changes to the Protocol following Institutional Review Board (IRB) approval affecting the safety of subjects, scope/objectives of the investigation, or the scientific quality of the study are documented as amendments. Such changes require P&G, Investigator, and IRB approval prior to implementation, unless immediate action is required to safeguard subject safety. Administrative/minor changes (e.g., typos, changes in P&G personnel [excluding medical monitor], etc.) are documented as revisions but do not have to be submitted as amendments unless required by the IRB. Any change in P&G's monitoring staff, Clinical Trial Manager or Medical Monitor during the conduct of the study, must be reported to the Investigator.

Serious Adverse Event Reporting

A *serious adverse event* is defined as an event, which suggests a definite hazard or handicap to the subjects. Serious adverse events are any events resulting in death, life threatening situation, disability or permanent damage, hospitalization or prolongation of existing hospitalization, or congenital anomaly/birth defects; events requiring intervention to prevent permanent impairment/damage; or other serious (important) medical events.

When an Investigator is notified of a serious AE, the Investigator must promptly (within 24 hours) notify the Sponsor (Clinical Trial Manager or the Medical Monitor) of the serious or unexpected event, regardless of causality. Within 5 working days, a written and/or electronic report describing the circumstances of the event must be submitted to the Sponsor. The Investigator will be responsible for SAE reporting to the IRB.

Study Medication Dispensing, Storage and Accounting

Study products are stored in a secure area, under environmental condition as required by label instructions or as described in the Protocol, and dispensed only under the authorization of the Investigator. The storage condition shall be properly documented. Both the receipt and dispensation of all test products (used and unused) are documented using forms provided by P&G or suitable forms provided by the site. Study products are returned to P&G following the trial, or alternatively, they are destroyed at the clinical site provided the site has an existing SOP for the destruction of clinical materials and prior written approval from P&G.

Study Termination

The study is terminated upon completion of all subject treatments and evaluation. The study may be discontinued at any time.

Subject Consent

The Investigator obtains written informed consent for each subject prior to that subject's participation in the study, per the US Code of Federal Regulations, Title 21, Parts 50.25 and 50.27 and ICH-GCPs, Chapter 4, subpart 4.8. Subjects, or their legal guardian, are required to read, sign and date an IRB approved consent form with the Investigator also maintaining a signed and dated copy. The subject or legal guardian will be given a copy of the consent form. All study procedures must be explained in non-technical terms.

APPENDIX II

Listing of Questionnaires

DMI Questionnaire

Subjects must answer 2 or more of the 4 questions positively in order to continue into the study.

How much do you agree or disagree that you experience the following? (strongly disagree, disagree, disagree a little, agree a little, agree, strongly agree)

- 1) No moisture in the mouth
- 2) Lips sticking to teeth
- 3) Tongue sticking to roof of mouth
- 4) Throat feels dry

Baseline MD Questionnaire

Subjects to answer:

- 1) How moist does your mouth feel now? (0=not at all to 10= very moist)
- 2) How dry does your mouth feel now? (0=very dry to 10=not dry at all)

Immediate MD Questionnaire

Subjects must answer:

- 1) How moist does your mouth feel now? (0=not at all to 10= very moist)
- 2) How dry does your mouth feel now? (0=very dry to 10=not dry at all)

Product Use Questionnaire

Considering everything about the mouthwash product you used today, please indicate the one word or phrase which best describes your overall opinion of this product. (Select one response)- excellent=5, very good=4, good=3, fair=2, poor=1

What are all the things you **LIKED** about the mouthwash product you used today? Please be specific. Free-form text

What are all the things you **DID NOT** like about the mouthwash product you used today? Please be specific. Free-form text

Considering your experience **while using** the mouthwash product you used today, how would you rate the mouthwash for each of the following characteristics? (Select one response for each attribute) excellent=5, very good=4, good=3, fair=2, poor=1:

- 1) Overall taste
- 2) Overall sweetness

- 3) Level of thickness to coat mouth tissue
- 4) Flavor strength
- 5) Soothes while I swish

Considering your experience **immediately after** using the mouthwash you used today, how would you rate the mouthwash for each of the following characteristics? (Select one response for each attribute- excellent=5, very good=4, good=3, fair=2, poor=1):

- 1) Leaves a cooling sensation in mouth
- 2) Freshens my breath
- 3) Leaves my whole mouth feeling protected
- 4) Leaves a pleasant taste in my mouth

Which of the following descriptors apply to the sample you just evaluated? (Circle all that apply):
Metallic, Medicinal, Thick, Burn, Tingle, Moisturizing, Chalky, Filmy, Sweet, Watery, Mild, Bitter, Sour, Soothing, Sharp, Fruity, Minty, Refreshing, Cooling, Slimy, Clean, Astringent, Harsh, Numbing, Dry, Bland, Oily, Smooth

PPAQ I/ MD Questionnaire

Since you have been used the product, please rate each of the following at this timepoint: (Select one response for each attribute)- excellent=5, very good=4, good=3, fair=2, poor=1:

- 1) Relieves the discomfort of your dry mouth
- 2) Feels comfortable in your mouth
- 3) Soothes your mouth
- 4) Allows you to speak without difficulty
- 5) Effectively moistens your mouth
- 6) Effectively lubricates your mouth
- 7) Helps to freshen your breath
- 8) Protects your mouth from drying out
- 9) Provides whole mouth comfort
- 10) Helps you to swallow without difficulty
- 11) Helps your mouth feel "normal"

Subjects must answer:

- 1) How moist does your mouth feel now? (0=not at all to 10= very moist)
- 2) How dry does your mouth feel now? (0=very dry to 10=not dry at all)

PPAQ II Questionnaire

Since you have been using the product over the last 4 days, please rate each of the following as they apply to the rinse study product: (Select one response for each attribute)- excellent=5, very good=4, good=3, fair=2, poor=1:

- 1) Provides relief all night
- 2) Reduces the number of times you wake up from dry mouth
- 3) Feeling less parched when you wake up
- 4) Having a long-lasting dry mouth relief

- 5) Having a long-lasting lubricating effect
- 6) Having a long-lasting moisturizing effect

4-hour Rating Questionnaire

- 1) How would you rate the overall moisturization of your mouth after using the product? 0= does not provide moisturization at all to 10=best possible moisturization
- 2) How would you rate the long-lasting moisturization effect of the product? 0= does not provide long lasting moisturization at all to 10=best possible long lasting moisturization
- 3) How would you rate the overall relief of your dry mouth after using the product? 0= does not provide relief at all to 10=best possible relief
- 4) How would you rate the long-lasting dry mouth relief of the product? 0= does not provide long lasting relief at all to 10=best possible long-lasting relief

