Each of the eligible subjects will be randomly assigned to one of the treatment sequences. Subjects will be assigned to a treatment sequence in the order they come to the site during their first Baseline visit using a Treatment Sequence Schedule. The site will keep the Treatment Sequence Schedule while the study is on-going. Should a subject miss a treatment period, that treatment in the sequence will be skipped.

10. Determination of Sample Size

Sample size is based on logistical considerations.

11. Safety Variables

Oral Examination

Assessment of the oral soft tissue is conducted via a visual examination of the oral cavity and perioral area utilizing a standard dental light, dental mirror, and gauze. The structures examined include the gingiva (free and attached), hard and soft palate, oropharynx/uvula, buccal mucosa, tongue, floor of the mouth, labial mucosa, mucobuccal/mucolabial folds, lips, and perioral area.

Assessment of the oral hard tissues are conducted via a visual examination of the dentition and restorations utilizing a standard dental light, dental mirror, and air syringe. All abnormal findings are recorded and categorized by their location with hard tissue findings categorized as “other-oral.” An AE is recorded if a new abnormal finding is noted after treatment application or any abnormal finding noted prior to treatment application increases in severity after treatment is applied.

12. Hypotheses

The following hypotheses will be tested for each response to the PPAQ I/ MD questions, the PPAQ II questions, and the rating questions at each applicable time point:

Null: The mean response is equal between the Experimental rinse and Water.

Alternative: The mean response is not equal between the Experimental rinse and Water.

Null: The mean response is equal between the Marketed rinse and Water.

Alternative: The mean response is not equal between the Marketed rinse and Water.

The primary endpoint will be the response to “relieving the discomfort of dry mouth” from the modified PPAQ I/ MD two hours after supervised product use on Day 4 of treatment. Responses to all other questions and time points will be of secondary interest.

13. Statistical and Analytical Plans

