Responses to the questions will be analyzed separately using a general linear mixed model for a crossover with period and treatment as fixed effects and subject as a random effect. Carryover will be assessed and if reasonably appropriate, it may be included in the statistical model. Statistical comparisons will be two-sided with a significance level of 0.10. No adjustments will be made for multiple comparisons. Additional analyses of the data may be performed. This may include but is not limited to area under the curve (AUC).

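### The secondary dryness item's numbers run against its question, so some subjects may reverse the scale and weaken the dryness contrasts; aligning the wording before printing is a cheap improvement

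*Combined protocol and SAP*

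**What the plan says.** Appendix II prints the item as "How dry does your mouth feel now? (0=very dry to 10=not dry at all" in three places: the Baseline MD, the Immediate MD and the PPAQ I/MD. On each form it follows the moistness item, "How moist does your mouth feel now? (0=not at all to 10= very moist".

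Section 12 sets the scope of testing: "The following hypotheses will be tested for each response to the PPAQ I/ MD questions, the PPAQ II questions, and the rating questions". The dryness item is part of the PPAQ I/MD and is therefore included. The Baseline MD and Immediate MD forms are not named there.

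The primary endpoint is a different item: "The primary endpoint will be the response to “relieving the discomfort of dry mouth” from the modified PPAQ I/ MD two hours after supervised product". Section 12 adds: "Responses to all other questions and time points will be of secondary interest". The dryness item is therefore secondary.

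Section 13 specifies a "general linear mixed model for a crossover with period and treatment as fixed effects and subject as a random effect", with no baseline covariate, and states: "Statistical comparisons will be two-sided with a significance level of 0.10". On power, Section 10 says only: "Sample size is based on logistical considerations".

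**The concern.** A subject who reads a question about how dry the mouth is, with a 0 to 10 scale, may expect a high number to mean very dry. If such a subject writes 8 for a very dry mouth, the record shows a mouth nearly free of dryness. The line above may encourage the slip: on the moistness item the zero end is the absence of the thing asked about, and on the dryness item that end moves to 10. Of the six distinct 0 to 10 items in Appendix II (moistness, dryness and the four 4-hour ratings), only the dryness item runs against its own question.

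A reversed answer is within range and does not look wrong by itself. The documents describe no instruction on scale direction and no comparison of the moistness and dryness answers. If reversal happens at the same rate under rinse and Water, it does not average out. It pulls the treatment difference toward zero and adds noise, in a trial of up to 30 subjects with no stated power margin.

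**Working it through.** **1. Forms per period (Table 1).** Baseline MD 1, Immediate MD 2 (Days 1 and 4), PPAQ I/MD at 30 minutes 2, and PPAQ I/MD at 1, 2 and 4 hours 3 x 2 = 6. The total is 1 + 2 + 2 + 6 = 11. The last 6 are completed off-site.

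**2. Contrasts exposed.** PPAQ I/MD: 4 times x 2 days x 2 comparisons (each rinse against Water) = 16. The Immediate MD form would add 1 x 2 x 2 = 4 if it is analysed. Baseline dryness is not in the Section 13 model.

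**3. Effect of reversal on the mean.** Let x be the true score and p the share of answers reversed, the same under each treatment.

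E[recorded] = (1 - p)x + p(10 - x) = (1 - 2p)x + 10p.

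The term 10p cancels between treatments, so a true difference d becomes (1 - 2p)d:
- p = 5%: 0.90d
- p = 10%: 0.80d
- p = 20%: 0.60d

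**4. Effect on power (illustration only).** The plan states no power figure to reproduce. From the documents: n = 30 and two-sided alpha 0.10 (z = 1.645). Assumed: p, and the ratio r of the true difference to the SD of the within-subject difference. The contrast is treated as a paired comparison, which approximates the three-period mixed model.

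If a share p of subjects reverses consistently, then in units of that SD the mean is (1 - 2p)r and the variance is 1 + 4p(1 - p)r². So

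Power = Φ(√30 x (1 - 2p)r / √(1 + 4p(1 - p)r²) - 1.645).

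Example, r = 0.5 and p = 10%: mean 0.8 x 0.5 = 0.40; variance 1 + 4 x 0.1 x 0.9 x 0.25 = 1.09; 0.40/√1.09 = 0.383; √30 x 0.383 = 2.098; 2.098 - 1.645 = 0.453; Φ = 0.675.

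| r (assumed) | p = 0 | 5% | 10% | 20% |
|---|---|---|---|---|
| 0.3 | 0.50 | 0.43 | 0.36 | 0.25 |
| 0.5 | 0.86 | 0.78 | 0.68 | 0.45 |
| 0.7 | 0.99 | 0.95 | 0.88 | 0.64 |

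**5. Reversal that comes and goes within a subject.** This was simulated with 20,000 trials of 30 paired scores for each p, rounded and held to 0-10. Assumed: true means 4 and 5, between-subject SD 1.5 and within-subject SD √2, so the SD of the difference is 2 and r = 0.5.

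| Reversal | p = 0 | 5% | 10% | 20% |
|---|---|---|---|---|
| Consistent within subject | 0.83 | 0.74 | 0.64 | 0.43 |
| Independent at each occasion | 0.83 | 0.68 | 0.55 | 0.33 |

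Occasional reversal costs more because, when only one of the two answers is flipped, the subject's own level no longer cancels from the difference.

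**The case against.** The strongest reply is that nothing is wrong with the scoring. Both anchors are part of the item, and a subject who uses them is recorded correctly. High means better on both MD items, on every PPAQ item and on all four 4-hour ratings, which is a coherent convention and could itself limit errors. Appendix II is only a listing of the questions; the layout that subjects see is not in the documents, so how misleading it looks cannot be judged. Nothing shows that any subject would misread the item, and p, the effect sizes and the SDs above are all assumed. Each period's first three forms are completed on-site, and Appendix I (Data Collection) has ambiguous values queried.

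Most of this stands. It rules out three stronger readings that a reader might infer:
- *The item is miscoded.* It is not; the anchors define the score.
- *The dryness results will be weakened.* The documents support only a risk, with no loss at p = 0.
- *The main result is threatened.* The primary endpoint is a 1 to 5 item that runs with its wording.

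What remains is the mismatch between stem and numbers. The general query rule does not clearly reach it, because a reversed in-range number is not ambiguous on its face. The common high = better convention does not remove it either, since a subject answers the question asked and need not know the scoring rule.

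**Conclusion.** The point holds as a low-severity wording risk on a secondary item. If answers are reversed at the same rate under rinse and Water, the expected contrast shrinks by 10%, 20% or 40% at p = 5%, 10% or 20%. With r = 0.5, power falls from 0.86 to 0.78, 0.68 or 0.45 when subjects reverse consistently; in the simulation, occasional reversal costs more. These figures show sensitivity and are not a forecast, because the documents supply neither p nor an effect size. The equal-rate assumption also matters: if rates differed by treatment, the term 10p would not cancel and the bias need not be toward zero.

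A reader might count 20 tested dryness contrasts by including the Immediate MD form, or treat the baseline score as part of the damage. Section 12 clearly names 16, and baseline dryness does not enter the specified model.

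**What to change.** Before printing, make question and numbers agree on all three forms while keeping the anchors, high = better scoring and analysis as they are. For example, open the stem with *How free of dryness* in place of the present first two words. Explain the scale direction in the same way to every subject before the first form is completed, and so before first product use.

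Do not have site staff prompt subjects to correct their scores. Under Section 7 the rinses are used for 30 seconds and the water is a single sip, so staff who supervise use can tell them apart; prompting changes to a subjective score could introduce bias.

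If a moistness/dryness consistency check is wanted, it should cover both directions of contradiction. A rule that looks only for high moistness with a low dryness-item score would miss a very dry mouth scored 8. Prespecify the check, run it masked to treatment, and use it only for a sensitivity analysis. It will miss many mid-scale reversals (a true 4 recorded as 6), so the rewording is the real remedy.

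The cost is one line on three forms and a short standard explanation. The downside is that the wording would no longer match any earlier use of the item. After IRB approval, the change process in Appendix I would apply.
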